1.0 Objectives*

1.1 The purpose of our research is to compare the effectiveness of 40mg/ml sodium thiosulfate (STS) solution to normal saline (0.9% sodium chloride) when injected intralesionally for the treatment of calcinosis cutis. Our specific aim is to assess the response of dystrophic and idiopathic calcinosis cutis to the injections of sodium thiosulfate in our patients.

1.2 Our hypothesis is that three injections of STS, each spaced one month apart, will significantly improve our patients' calcinosis cutis condition to a point where they are effectively clear or have a 2-point improvement in their Physician Global Assessment (PGA) scores when compared to normal saline.

2.0 Background*

2.1 Calcium plays an important role in the growth and differentiation of the skin.¹ As a result, dysregulation of calcium can have dermatologic consequences. One of these consequences results in a condition known as calcinosis cutis. This is an uncommon dermatologic condition in which calcium deposits are formed in the skin and result in cutaneous calcification. There are various types of this condition, including dystrophic, metastatic, iatrogenic, and idiopathic.^{1,2} Our research, however, will be focused on dystrophic and idiopathic calcinosis cutis. These forms often present in areas of the skin that have been previously damaged, and these patients often have no fundamental metabolic irregularities in calcium regulation.¹ It is believed that the calcification develops when an associated disease causes tissue damage. This damage allows calcium to move into the affected area and crystallize.¹ Another line of thinking is that the acidity which follows cell damage may have an effect on local calcium inhibitory processes.¹ Dystrophic Calcinosis cutis is commonly associated with autoimmune connective tissue disorders such as scleroderma, dermatomyositis, and cutaneous lupus erythematosus.^{1,2} Other etiologies may include panniculitis, genetic disorders, infections, neoplasms, and trauma¹.

2.2 There are a variety of potential treatments for dystrophic calcinosis cutis which depends upon factors such as size, location, and etiology. These treatments include surgical excision, bisphosphonates, warfarin, tumor necrosis factor inhibitors, among others². However, these often have varying degrees of success and none of which are FDA-approved.² One studied treatment involves the drug sodium thiosulfate. Sodium thiosulfate (STS) has been used successfully in a number of cases topically, intravenously (IV), and intralesionally by increasing the solubility of the cutaneous calcium deposits. There have been several case reports examining STS topically for several months.³⁻⁷ Potential downsides to topical treatments are that they may not penetrate the skin deep enough to affect the calcifications, and patients must strictly adhere to the application directions. Additionally, STS has been used intravenously with success.^{3,8,9} However, there have been cases of patients discontinuing IV STS due to its side effects of fatigue and nausea.¹⁰ There have also been cases in which there was a lack of response to IV STS.^{9,10}

A Comparative Study of the Efficacy of Intralesional Sodium Thiosulfate Versus Intralesional Normal Saline for the Treatment of Dystrophic and Idiopathic Calcinosis Cutis, A Double-Blind Randomized Placebo-Controlled Trial

2.3 We wish to examine STS intralesionally (IL) since this would allow for minimization of the side effects of the IV treatment, higher local concentrations than the topical approach, and easier accessibility of the affected site(s). Intralesional STS has been used in a number of cases to treat dystrophic calcinosis cutis with great success.¹¹⁻¹³ However, from the literature, there are currently no prospective studies which compare the efficacy of STS to normal saline which is the gap in knowledge that we are attempting to address.

Our prospective study will allow us to address this gap in knowledge by comparing the intralesional administration of STS to normal saline for the treatment of dystrophic and idiopathic calcinosis cutis lesions. If successful, this study will contribute significantly to demonstrating the efficacy of IL STS for dystrophic and idiopathic calcinosis cutis and could be a stepping stone for development of more effective treatments.

3.0 Inclusion and Exclusion Criteria*

3.1 Subjects will be screened in person at the UCF Health Clinic in Lake Nona. Subjects will be screened and evaluated in the clinic to verify diagnosis through history, physical findings, health records, and previous labs. Subjects who fit the diagnosis of dystrophic or idiopathic calcinosis cutis will be asked whether they wish to participate in the study. Subjects will not be recruited from a search of their medical records (see Section 22: Recruitment Methods). Female subjects who require a urine pregnancy test as part of their screening will be asked to give verbal informed consent for the test prior to the completion of screening.

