3.2 Screening Criteria

- Inclusion Criteria:
 - Male or female adult 18 years of age or older
 - Must have health insurance will be eligible to participate
 - Must have a current diagnosis of dystrophic or idiopathic calcinosis cutis
 - Subjects must have at least 2 lesions of at least 2mm in size

- Exclusion Criteria:
 - Unable to read and speak English
 - Allergy to any component of the sodium thiosulfate solution
 - Adults unable to consent
 - Individuals who are not yet adults (infants, children, teenagers)
 - Pregnant women
 - Women who are breastfeeding
 - Prisoners

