4.0 Study-Wide Number of Subjects*

A Comparative Study of the Efficacy of Intralesional Sodium Thiosulfate Versus Intralesional Normal Saline for the Treatment of Dystrophic and Idiopathic Calcinosis Cutis, A Double-Blind Randomized Placebo-Controlled Trial

4.1. We plan on enrolling 12 subjects with the aim to accrue 10 subjects who successfully screen for eligibility for the study. This number was derived on consultation with [name].

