7.0 Study Timelines*

7.1 Subjects are expected to participate in this study for a total of three months. During these three months, subjects will be required to come to UCF Health Clinic at [name] for a total of four appointments:

- Timeline:
 - Week 0 (Visit 1): 90 minutes
 - 48-hour post-treatment follow-up phone call: 5 minutes
 - Week 4 (Visit 2): 90 minutes
 - Week 8 (Visit 3): 90 minutes
 - Week 12 (Visit 4): 15 minutes
- Ten months is the anticipated length of time to recruit subjects
- The study is expected to be completed by April 2019.

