8.2 Primary and secondary safety endpoints

- Primary safety endpoints: Serious adverse event due to IL STS, will be required to withdraw.
- Secondary safety endpoints:

A Comparative Study of the Efficacy of Intralesional Sodium Thiosulfate Versus Intralesional Normal Saline for the Treatment of Dystrophic and Idiopathic Calcinosis Cutis, A Double-Blind Randomized Placebo-Controlled Trial

- Intolerance to pain associated with injections, will be required to withdraw.
- Vasovagal reaction. If a subject develops a vasovagal reaction, he or she will be given the option to withdraw but will not be required to withdraw.
- If a subject experiences a mild to moderate adverse event he or she will be given the option to withdraw but will not be required to withdraw.

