9.2 Timeline

- Subject visits
 - The sodium thiosulfate and saline solution will be prepared the same day as the subject's baseline visit after consent to participate is obtained.
 - Baseline Visit
 - Minute 00-15:
 - Informed consent, HIPAA authorization, and screening and enrollment process.
 - Minute 15-30:
 - Obtain demographics and medical history via Demographics Form and Medical History Form (attached)
 - Selection of 2 lesions of dystrophic or idiopathic calcinosis cutis.
 - Note: The lesions must be at least 2mm in diameter and no larger than 2cm in diameter. If a lesion smaller than 2cm is not available then a 2 cm x 2 cm portion of a larger lesions will be used.
 - One lesion will be "Lesion A", and the other will be "Lesion B" for the entire study duration.
 - Lesions will be labeled with their corresponding letter 'A' and 'B' with a marker and photographed
 - Assessment of calcinosis cutis lesions via Case Report Form (see attached).
 - Administration of STS and normal saline.
 - Minute 30-90:
 - Monitoring of subject for adverse events
- 48-hour follow-up phone call:
 - Minute 0-5:
 - Brief phone call to assess for any adverse reactions

A Comparative Study of the Efficacy of Intralesional Sodium Thiosulfate Versus Intralesional Normal Saline for the Treatment of Dystrophic and Idiopathic Calcinosis Cutis, A Double-Blind Randomized Placebo-Controlled Trial

-
- 1-month (+/- 8 days) Follow-up
 - Minute 00-30:
 - Lesions will be labeled with their corresponding letter 'A' and 'B' with a marker and photographed
 - Assessment of calcinosis cutis via Case Report Form (attached)
 - Administration of STS and normal saline.
 - Minute 30-90:
 - Monitoring of subject for adverse events
 - Debrief of subject
- 2-month (+/- 8 days) Follow-up
 - Minute 00-30:
 - Lesions will be labeled with their corresponding letter 'A' and 'B' with a marker and photographed
 - Assessment of calcinosis cutis via Case Report Form (attached)
 - Administration of STS and normal saline
 - Minute 30-90:
 - Monitoring of subject for adverse events
 - Debrief of subject
- 3-month (+/- 8 days) Follow-up
 - Minute 00-15:
 - Lesions will be labeled with their corresponding letter 'A' and 'B' with a marker and photographed
 - Assessment of calcinosis cutis via Case Report Form (attached)

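### In the text shown, pregnancy is tested only at screening and no stopping rule names it, so STS injections 2 and 3 have no visible re-check (minor, precautionary)

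*Combined protocol and SAP*

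**What the plan says.** **Testing.** Section 3.1 describes "Female subjects who require a urine pregnancy test as part of their screening" and asks them for verbal consent to it. Section 3.2 lists "Pregnant women" among the exclusions. The screening and consent steps in 9.2 have the test done where necessary, when the eligibility items are completed. Section 23.2 expects that it may produce a few screen failures. Screening takes up the first 15 minutes of the baseline visit, at which injection 1 is also given.

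**Later doses.** Section 1.2 plans "three injections of STS, each spaced one month apart". Section 7.1 schedules "Week 4 (Visit 2): 90 minutes" and "Week 8 (Visit 3): 90 minutes", and 9.2 allows 8 days either side. At both visits 9.2 lists labelling and photographs, the Case Report Form, the injections, monitoring and a debrief. It lists no pregnancy test.

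**Stopping.** Section 8.2 gives one ground for mandatory withdrawal as "Serious adverse event due to IL STS, will be required to withdraw" and another as intolerance of injection pain. Withdrawal is optional after a vasovagal reaction or a mild to moderate adverse event. Section 13.1 names treatment intolerance and anxiety. Section 12.1 suspends the study if treated lesions show significantly more severe adverse events than control lesions. None of these names pregnancy, and the text shown has no contraception requirement.

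**Risk.** Section 14.1 places STS in Pregnancy Category C, notes the lack of adequate controlled studies in pregnant women, and restricts use in pregnancy to cases where the benefit warrants the fetal risk.

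**The concern.** The caution in 14.1 concerns dosing during pregnancy, so it applies to all three injections. In the text shown, the plan acts on it before the first injection only. A woman who conceives after Week 0, or whose pregnancy was too early to detect at screening, could receive one or two further STS injections while the visible schedule is followed exactly. A known pregnancy might come up in the adverse event questions asked at each visit, but the text does not say what should then happen to dosing. An unrecognised pregnancy has no visible route to detection.

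What is at stake is a small, avoidable exposure. The randomisation, the endpoints and the efficacy comparison are not involved.

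**Working it through.** The plan states no age for the pregnancy result, so there is no figure to reproduce. The inputs are the Week 4 and Week 8 visits (7.1), the 8-day window (9.2), and a test on day 0 because screening is part of the baseline visit (9.2).

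**Age of the result** = nominal visit day minus or plus the window. The protocol does not say what the windows are counted from, so four variants are shown.

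| Assumption | Injection 2 (days) | Injection 3 (days) |
|---|---|---|
| 28-day months, from baseline | 28 - 8 = 20 to 28 + 8 = 36 | 56 - 8 = 48 to 56 + 8 = 64 |
| Calendar months (28-31; 59-62), from baseline | 28 - 8 = 20 to 31 + 8 = 39 | 59 - 8 = 51 to 62 + 8 = 70 |
| 28-day months, from previous visit | 20 to 36 | 20 + 20 = 40 to 36 + 36 = 72 |
| Calendar months, from previous visit | 20 to 39 | 20 + 20 = 40 to 39 + 39 = 78 |

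In every variant the result is at least 20 days old at injection 2 and at least 40 days old at injection 3. A test on the day of injection would make it 0 days. These ages apply only to women who were tested. They are not probabilities of exposure.

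**Dose** (9.2):
- Largest dose per visit: 0.1 ml/cm² x (2 cm x 2 cm) = 0.4 ml, and 0.4 ml x 40 mg/ml = 16 mg, as the protocol states.
- Largest dose over injections 2 and 3: 2 x 16 = 32 mg. Smaller lesions receive less.

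**Comparison with the animal data** (14.1). The maternal doses without embryotoxic or teratogenic effect ran up to 550, 400, 400 and 580 mg/kg/day in four species, so 400 is the lowest of four upper limits. The protocol gives no body weight, so 50-90 kg is assumed:
- 16 / 50 = 0.32 mg/kg, and 400 / 0.32 = 1,250.
- 16 / 90 = 0.178 mg/kg, and 400 / 0.178 = about 2,250.

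The largest single dose is therefore roughly 1,250 to 2,250 times below that limit in plain mg/kg. The ratio sets one monthly injection against daily dosing and makes no adjustment between species, so it shows only the order of size.

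**Extra tests.** Section 4.1 plans enrolment "with the aim to accrue 10 subjects who successfully screen for eligibility". If all 10 were women of childbearing potential, 10 x 2 = 20 tests. If all 12 enrolled subjects qualified, 12 x 2 = 24.

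**The case against.** **The check may exist elsewhere.** The Case Report Form is completed before the injection at both later visits, and 9.2 refers to an eligibility portion of a form of that name. There is also a separate Eligibility Form, and the consent is a natural place for a pregnancy instruction. None of these is available here, so a reader might wrongly infer that the trial has no re-check at all. The documents support only the statement that none is visible. However, the protocol describes the Case Report Form at those visits as an assessment of the lesions, and it ties eligibility to screening.

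**Urine disposal.** Section 9.2 provides for disposing of urine samples, just after the administration steps and without mention of screening. That line schedules no test.

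**14.1 already covers a known pregnancy.** Its caution is not limited to entry, and a board-certified dermatologist gives every injection. This has force: a recognised pregnancy would probably prompt a decision not to inject. It does not help with an unrecognised one, and a stated rule would still be clearer than reliance on judgement.

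**The harm is very small.** This stands. The dose is low, the reported animal findings are reassuring, and the number of women concerned is not given and could be zero.

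**Conclusion.** The point holds as a cheap, precautionary safety improvement of minor severity. On the text shown, the plan could re-dose an unrecognised pregnancy, and nothing says what to do about a recognised one.

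The 20-36 and 48-64 day figures assume 28-day months counted from baseline. The other conventions shift the ranges without changing the conclusion.

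Three stronger readings are tempting but unsupported:
- **A breach of the exclusion criterion.** Pregnancy is listed as a screening criterion and governs entry only, so later dosing does not contradict it.
- **Demonstrated fetal harm.** The lead-in to the pregnancy text in 14.1 speaks of known harm, but the paragraphs under it report none. They give a category, a lack of human data and reassuring animal results.
- **An effect on the trial's efficacy results.** No efficacy endpoint, allocation step or efficacy analysis depends on this.

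**What to change.** First check the attached Case Report Form, the Eligibility Form and the consent. If they already contain a pregnancy check before each injection and an instruction to stop, nothing needs to change. Otherwise:

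1. **Sections 3.1 and 9.2.** Define women of childbearing potential once in 3.1, so that the same group is tested at entry and later. In 9.2, add a urine pregnancy test for them before injection at the 1-month and 2-month visits.
2. **Section 13.1.** State that a known or detected pregnancy stops further injections while follow-up assessments continue. Do not call this withdrawal, because 13.3 ends data collection on withdrawal.
3. **Recording.** Note the pregnancy, and the number of injections received, in the subject's file. Keep the pregnancy apart from the lesion-level adverse events compared under 12.1: each subject carries both a treated and a control lesion, so it cannot be assigned to either.

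The cost is at most two urine tests per woman concerned, at visits already scheduled and with a test already in use: 20 tests for 10 eligible subjects, or 24 if all 12 qualify. A subject who becomes pregnant may lose later injections, so her remaining assessments would reflect incomplete treatment. A urine test could still miss a very early pregnancy, so the change narrows the gap without closing it.

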3.2 Screening Criteria

- Inclusion Criteria:
 - Male or female adult 18 years of age or older
 - Must have health insurance will be eligible to participate
 - Must have a current diagnosis of dystrophic or idiopathic calcinosis cutis
 - Subjects must have at least 2 lesions of at least 2mm in size

- Exclusion Criteria:
 - Unable to read and speak English
 - Allergy to any component of the sodium thiosulfate solution
 - Adults unable to consent
 - Individuals who are not yet adults (infants, children, teenagers)
 - Pregnant women
 - Women who are breastfeeding
 - Prisoners

4.0 Study-Wide Number of Subjects*

A Comparative Study of the Efficacy of Intralesional Sodium Thiosulfate Versus Intralesional Normal Saline for the Treatment of Dystrophic and Idiopathic Calcinosis Cutis, A Double-Blind Randomized Placebo-Controlled Trial

4.1. We plan on enrolling 12 subjects with the aim to accrue 10 subjects who successfully screen for eligibility for the study. This number was derived on consultation with [name].

5.0 Study-Wide Recruitment Methods*

5.1 Not applicable. This is not a multicenter research study and research will only be conducted at the UCF Health clinic in Lake Nona. Local recruitment methods are described in section 19.0 Setting.

6.0 Multi-Site Research*

6.1 Not applicable. This is not a multi-site research project. Research will only be conducted at the UCF Health clinic in Lake Nona.

7.0 Study Timelines*

7.1 Subjects are expected to participate in this study for a total of three months. During these three months, subjects will be required to come to UCF Health Clinic at [name] for a total of four appointments:

- Timeline:
 - Week 0 (Visit 1): 90 minutes
 - 48-hour post-treatment follow-up phone call: 5 minutes
 - Week 4 (Visit 2): 90 minutes
 - Week 8 (Visit 3): 90 minutes
 - Week 12 (Visit 4): 15 minutes
- Ten months is the anticipated length of time to recruit subjects
- The study is expected to be completed by April 2019.

8.0 Study Endpoints*

8.1 Study endpoints:

- Primary:
 - Change in size of study lesions
 - Change in Physician Global Assessment
 - Visual Analog Scale of pain of injection
- Secondary:
 - Adverse Events

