- During each visit subjects will be monitored for any adverse events and asked about any potential adverse events since the last visit. Any adverse events will be logged on the Adverse Events Form (see attached).
- Visit 1 will be followed with a 48-hour post-treatment phone call to assess for any adverse events.
- After all subjects have completed their participation, photographs of lesions will be reviewed by [name] who will fill out the Independent Observer Case Report Form (see attached) for each visit. He will be blinded as to which lesions received which treatment and at which visit in the study the lesions were photographed.
- Screening and consent
 - First, each subject will sit down with the principal investigator to discuss the study in depth and review the screening criteria. After all risks, benefits, alternatives, and questions have been discussed consent will be obtained.
 - After the informed consent form is signed, the eligibility screening portion of the case report form will then be filled out by the principal investigator with the research subject. If necessary, a pregnancy test will be performed.

A Comparative Study of the Efficacy of Intralesional Sodium Thiosulfate Versus Intralesional Normal Saline for the Treatment of Dystrophic and Idiopathic Calcinosis Cutis, A Double-Blind Randomized Placebo-Controlled Trial

- Solution preparation
 - 50 ml vials of sodium thiosulfate (250mg/ml) will be used for preparation of the treatment solution.
 - The solution from the bottle will be diluted in a ratio of 1 part sodium thiosulfate 250mg/ml to 5.25 parts sterile water to yield a 40mg/ml solution of sodium thiosulfate.¹⁴ This is done to make the final solution as close to isotonic as possible.
 - 30 ml vials of sodium chloride 0.9% will be used for the control treatment.
 - The solutions will be drawn up in 1 cc syringes utilizing a 25g needle by [name]. The needle will then be replaced with a capped 30g ½ inch needle.
 - All solutions will be drawn up by [name] the day of use and discarded immediately after use.
 - Treatment and control will be randomized once for the entire study and all subjects based upon a one-time flip of a coin as follows:
 - If coin flip is heads: all “A” lesions will receive STS and all “B” lesions will receive normal saline
 - If coin flip is tails: all “A” lesions will receive normal saline and all “B” lesions will receive STS
 - This result will be recorded on the Unblinded Treatment Document (See attached).

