 - [name] will not be notified of the result until after completion of the study so as to keep him blinded.
 - The syringes will be labeled with an “A” or “B” label for blinding by [name], or [name].

- Administration of study solutions
 - A volume of 0.1 ml/cm² of normal saline or STS will be injected into each lesion. Therefore, a maximum of 0.4ml of 40mg/ml STS or 16mg of STS (given maximum size of 2 cm x 2 cm) will be used per visit per subject.
 - The same treatment lesion will be injected only with STS every injection and the same control lesion will be injected only with normal saline (0.9% sodium chloride) every injection. In other words, “Lesion A” will always be injected with solution A and “Lesion B” will always be injected with solution B.
 - [name], a board-certified dermatologist, will be administering all injections of STS and normal saline to minimize risks for subjects.

- Disposal Protocol:
 - After use, needles will be disposed of in red sharps container according to UCF Health policy
 - After use, urine samples will be disposed of in the toilet according to UCF Health policy

A Comparative Study of the Efficacy of Intralesional Sodium Thiosulfate Versus Intralesional Normal Saline for the Treatment of Dystrophic and Idiopathic Calcinosis Cutis, A Double-Blind Randomized Placebo-Controlled Trial

9.3 Risk Management:

- Subjects will be directly observed during the administration of the STS and normal saline for any adverse events. An anaphylaxis kit is available in clinic should any subject experience such an event. The principal investigator is certified in basic cardiopulmonary life support and an AED is present in the facility. Subjects will be provided with the phone number of the PI should any issues related to participation in the study arise.
- Sodium thiosulfate is currently FDA-approved for as an antidote in the treatment of cyanide poisoning. FDA phase III studies are currently being conducted for use in calciphylaxis.
- 0.9% Sodium chloride is currently FDA-approved for parenteral replenishment of fluid, diluting or dissolving drugs for intravenous, intramuscular or subcutaneous injection, according to instructions of the manufacturer of the drug to be administered.
- Sterile water is currently FDA-approved as a solvent or diluent vehicle for parenterally administered drugs or solutions and as a source of water for parenteral fluid replenishment after suitable additives are introduced.

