9.4 Data to be collected

- Age
- Gender
- Race
- Ethnicity
- Medical History
 - Past Medical and Surgical History
 - Medications

A Comparative Study of the Efficacy of Intralesional Sodium Thiosulfate Versus Intralesional Normal Saline for the Treatment of Dystrophic and Idiopathic Calcinosis Cutis, A Double-Blind Randomized Placebo-Controlled Trial

- Allergies
- Social History
 - Tobacco use
 - Alcohol use
- Laboratory Results
- Size of lesions
- Visual Analog Scale for Pain (VAS Pain)
- Physician Global Assessment (PGA)
- Photographs will also be taken of all study lesions during every assessment and will be stored directly in the password protected HIPAA compliant network drive for clinical research at UCF Health. Though the photos will not contain any identifiers, subjects are potentially identifiable from the photos and thus they will be stored in the password protected HIPAA compliant network drive for clinical research at UCF Health.

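### The lesion-size primary endpoint names no scale or visit and its analysis has no baseline adjustment, although lesions may span 2 to 20 mm and pairs are not size-matched: define it relative to baseline and compare within subject

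*Combined protocol and SAP*

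**What the plan says.** **Endpoint.** Section 8.1 gives "Change in size of study lesions" as the first of three primary endpoints. It does not say whether size means diameter or area, whether change is absolute or relative, or which visit counts. Section 9.4 lists "Size of lesions" among the data collected, and section 9.2 schedules a lesion assessment at baseline and at each later visit.

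**Lesions.** Eligibility in section 3.2 sets only a lower limit: "Subjects must have at least 2 lesions of at least 2mm in size". Section 9.2 narrows the choice: "The lesions must be at least 2mm in diameter and no larger than 2cm in diameter". For subjects with only larger lesions it adds: "If a lesion smaller than 2cm is not available then a 2 cm x 2 cm portion of a larger lesions will be used". The pairing step reads only "Selection of 2 lesions of dystrophic or idiopathic calcinosis cutis". It asks for no match on size and gives no rule for which lesion is lettered A.

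**Allocation.** Section 9.2: "Treatment and control will be randomized once for the entire study and all subjects based upon a one-time flip of a coin as follows". All A lesions therefore receive one solution and all B lesions the other.

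**Analysis.** Section 11.1 plans descriptive summaries, then exploratory non-parametric tests at the 0.05 level, with Kruskal-Wallis and Mann-Whitney as examples. It mentions no paired test, baseline adjustment or percent change. The target in section 4.1 is 10 eligible subjects from 12 enrolled.

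**The concern.** On a raw scale the same number can stand for very different outcomes. A 2 mm lesion that vanishes changes by 2 mm, and so does a 20 mm lesion that shrinks by 10%.

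Two things are at stake. The first is precision: with 10 pairs, variation in baseline size adds noise to a raw treatment contrast. The second is validity. Suppose the investigator tends to letter the more prominent lesion A. One coin flip then puts the larger lesions on the same solution in every subject. If both lesions shrink by the same proportion, the larger ones lose more millimetres and a treatment difference appears where there is none. For example, if 15 mm and 5 mm lesions both shrink by 20%, the raw changes are 3 mm and 1 mm, while the relative changes are equal.

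Because the scale is open, it could also be chosen after the data are seen.

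**Working it through.** **Range.** The permitted diameter ratio is 20 mm / 2 mm = 10. For like shapes the area ratio is 10² = 100. These are permitted limits, not the expected spread.

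**The plan's own figures.** Section 9.2 scales the injection to area: "A volume of 0.1 ml/cm² of normal saline or STS will be injected into each lesion". The maximum reproduces: 0.1 ml/cm² × 4 cm² = 0.4 ml, and 0.4 ml × 40 mg/ml = 16 mg. The sample size of 10 cannot be reproduced, because no effect size, standard deviation or power is given.

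**Simulation 1 (all inputs assumed).** 10 pairs; independent diameters, log-uniform on 2 to 20 mm; follow-up diameter = baseline × shrinkage factor × log-normal noise with log SD 0.25; two-sided signed-rank test at 0.05. Raw change was compared with the log ratio.

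*Power, STS to 60% and saline to 90% of baseline:*

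| Measurement error SD per visit | Raw change | Log ratio |
|---|---|---|
| none | 0.60–0.62 | 0.88–0.89 |
| 0.5 mm | 0.56 | 0.70 |
| 1 mm | 0.43–0.45 | 0.43 |
| 1.5 mm | 0.33 | 0.29 |

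With diameters of 5 to 15 mm and no measurement error, power is 0.80 against 0.89.

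*Null rejection, same shrinkage in both lesions, no measurement error:*

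| STS lesion is the larger in | Raw, both × 0.8 | Raw, both × 0.7 | Log ratio |
|---|---|---|---|
| 80% of subjects | 0.10 | 0.16 | about 0.05 |
| all subjects | 0.20 | 0.40–0.41 | about 0.05 |

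With 1 mm measurement error the raw-change rates across these cases are 0.08 to 0.29, and the relative scale stays at about 0.05. With diameters of 5 to 15 mm and the STS lesion always the larger, raw change gives 0.09 to 0.19. The Mann-Whitney test, which the plan names, shows the same pattern: without measurement error, power is 0.69 against 0.91, and null rejection on raw change reaches 0.35.

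**Simulation 2 (a different model, also assumed).** 10 pairs; proportional shrinkage averaging 30% for STS and 10% for saline; lettering unrelated to size; signed-rank power.

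| Diameters | SD of shrinkage | Measure | Raw change | Percent change |
|---|---|---|---|---|
| 2–20 mm | 15 points | area | 0.29–0.38 | 0.75–0.76 |
| 2–20 mm | 15 points | diameter | 0.47–0.54 | 0.74 |
| 2–20 mm | 30 points | area | 0.15–0.17 | 0.24–0.26 |
| 8–12 mm | 15 points | area | 0.68 | 0.73 |
| 8–12 mm | 15 points | diameter | 0.72 | 0.74 |

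Matching pairs on size raises power on raw area change from 0.29–0.38 to 0.63–0.65 (2–20 mm, SD 15 points). With no mean change in either lesion, null rejection was 0.04 to 0.06 throughout.

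**Dependence on baseline.** In scenarios with a treatment effect (the one above, plus 50% against 10% shrinkage with SD 20 points), baseline size explains 28–78% of the variance of raw area change in STS lesions over 2–20 mm, and 15–64% for diameter. Over 8–12 mm the shares are 4–24% and 1–8%. For the within-pair contrast over 2–20 mm, the baseline size difference explains 7–45%.

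**The case against.** The strongest reply is that the protocol never chose raw change. A reader might infer that it did, but percent change and log ratio are changes too, and no section says absolute. The Case Report Form, an attachment that was not available, may define the measurement. This stands: the defect is an open scale that permits raw change. A form that defined the measurement would still leave the endpoint and analysis text without a scale.

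A reader might also infer that raw change mostly reflects baseline size. That is not supported as a general statement: the share for the within-pair contrast is below half in every scenario, and small if lesions are of similar size.

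The power advantage is partly built into models with purely proportional shrinkage and noise. This stands: with about 1 mm of measurement error it is gone.

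The false-positive figures need lettering that follows size and shrinkage of saline lesions as well. No section says that A is the larger lesion, and with lettering unrelated to size the rate is nominal. The coin is also as likely to give the larger lesions saline, so about half of such false positives would favour STS. This stands for the direction, but not for the two-sided error rate: a single flip shifts all subjects the same way, so nothing averages out. The single flip is the root of that risk and a separate allocation issue; a relative scale removes this particular consequence.

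Finally, section 1.2 frames the hypothesis on clearance or a 2-point PGA improvement, and section 11.1 calls the testing exploratory. That limits the impact, but size is still listed first among the primary endpoints.

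**Conclusion.** The concern holds in a conditional form. The plan leaves the scale and visit of a primary endpoint open, names only unpaired tests without baseline adjustment, and allows a tenfold diameter range with no size matching and no lettering rule.

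If raw change is then used, there are two consequences. Power falls when measurement error is small relative to lesion size, by amounts from almost nothing (8–12 mm lesions) to more than half (area over 2–20 mm). Null rejection rises to about 0.08–0.41 if the STS lesion is the larger in 80–100% of subjects and both lesions shrink by 20–30%, against about 0.05 on a relative scale.

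All these figures are illustrative, because the documents give no size distribution, variance or measurement error. They do not show that the trial will use raw change, that lettering will follow size, or that the error rate is inflated otherwise. The point is a recommended improvement rather than a fatal flaw.

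**What to change.** - **Sections 8.1 and 11.1, endpoint.** Name the size measure (diameter or area) and define the endpoint as change from baseline to Week 12 relative to baseline size. Percent change is the simpler choice: a resolved lesion scores −100% whatever its starting size, so no floor is needed. A log ratio needs a pre-stated floor and a sensitivity analysis on it. With a floor of 0.5 mm, clearance scores ln(0.5/20) = −3.69 for a 20 mm lesion but ln(0.5/2) = −1.39 for a 2 mm lesion.
- **Section 11.1, analysis.** Compare STS with saline by the within-subject difference, using the signed-rank test and its confidence interval. Report absolute change descriptively.
- **Section 9.2, selection.** Where more than two lesions are eligible, prefer the pair closest in baseline size. Where only a portion of a larger lesion is studied, say whether the portion or the whole lesion is measured.

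**Cost.** The first two changes need a few sentences and no new data, since size is already assessed at baseline and at each visit. The third is a small procedural change. The downside is that relative change is noisier for lesions near 2 mm, and its power advantage disappears if measurement error is about 1 mm.
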